Appendix 8.1.4. Medicated Topical Background Therapy-Free days defined by EASI-75

The definition is similar to Section 6.2.2.4 definition however EASI-75 will be used instead of EASI-90. The analyses method will be the same.

Appendix 8.2. Analyses

Appendix 8.2.1. Descriptive Summaries

At Baseline (doesn't apply to CFB or PCFB) and Weeks 2, 4, 8, 12, 16, 20 and 26 (unless otherwise specified), the number, mean, standard deviation, median, first and third quartiles will be presented for the absolute value, change from baseline and percent change from baseline in

- %BSA
- EASI by body region

- Weeks 1 ~ 26 PP-NRS (based on weekly average)

The difference between the following measures can be derived for each subject at Baseline and Weeks 2, 4, 8, 12, 16, 20 and 26. The number, mean, standard deviation, median, first and third quartiles will be presented at each treatment arm, and the treatment arms combined:

- PP-NRS (original) - PP-NRS (based on weekly average)
- EASI (original) - EASI (excluding scalp, palms and soles of feet)

Categorical summary will be provided for IGA.

Descriptive summary of change from baseline in HCRU.

Appendix 8.2.2. Binary endpoints

- Endpoints:
 - Weeks 2, 4, 8, 12, 16, 20 and 26 EASI-100, SCORAD75 (75% improvement from baseline), SCORAD90 (90% improvement from baseline), IGA of “Clear” Response
 - Weeks 2, 4, 8, 12, 16, 20 and 26 %BSA < 5%, PP-NRS <2, SCORAD (VAS) of Sleep Loss <2 Response
 - Weeks 1 ~ 26 PP-NRS4 (based on weekly average)
 - Weeks 2, 4, 8, 12, 16, 20 and 26 EASI-75, EASI-90, %BSA < 5% Response based on EASI (excluding scalp, palms and soles of feet) and %BSA (excluding scalp, palms and soles of feet)
 - Weeks 2, 12, 16, 20 and 26 DLQI < 2 Response
 - Weeks 12, 16 and 26 HADS Anxiety <8 Points, HADS Depression <8 Points Response
 - Weeks 12, 16 and 26 POEM \geq 4 points improvement from baseline, POEM <3 Response
 - Weeks 2, 12, 16, 20 and 26 Response based on achieving at least a 4-point improvement in the Skin Pain NRS
 - Baseline, Weeks 12, 16 and 26 Response based on achieving MOS-Sleep Scale Optimal Hours Slept Score of 1.
- Estimand strategy: Estimand 1, composite estimand.

- Analysis set: FAS (Section 4).
 - Analyses for binary endpoints that are defined based on reaching a threshold of absolute level (eg, PP-NRS <2) or change from baseline (eg, POEM ≥ 4 points improvement from baseline) will also require baseline value to be equal to or greater than that threshold (eg, for PP-NRS <2 , the baseline value needs to be ≥ 2 ; for POEM ≥ 4 points improvement, the baseline value needs to be ≥ 4 points) to be included in the analysis.
- Analysis methodology: CMH and normal approximation in Section 5.2.1.

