8.1.6.7. Medical Outcomes Study (MOS) Sleep Scale

The Medical Outcomes Study Sleep Scale (MOS-Sleep) is a validated 12-item measure used to assess sleep quality in the pastweek. The instrument has been validated for use by participants 18 years and older.⁴¹

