2.2. Study Design

This is a randomized, double-blind, double-dummy, active controlled, multi-center study to assess the efficacy and safety of abrocitinib 200 mg QD compared with dupilumab (administered per label guidelines) in adult participants on background topical therapy, with moderate to severe AD. The treatment duration is 26 weeks. A total of approximately 600 participants will be enrolled from approximately 220 sites globally. There are primary efficacy assessments at Week 2 and Week 4, and a key secondary efficacy assessment at Week 16. Efficacy and safety endpoints will be assessed throughout the entire study. Participants who complete the study through the Week 26 visit and are deemed eligible will enter the long-term extension (LTE) Study B7451015. A study design schematic is presented in [Figure 1](#).

Figure 1 Study Design Schematic

Study Treatments

- Group 1 (N=300): Abrocitinib 200 mg (2 x 100 mg tablets) administered orally QD and dupilumab-matching placebo administered by subcutaneous injection every other week (2 injections at baseline; to dummy the loading dose) from Day 1 to Week 26 (the last injection of dupilumab-matching placebo will occur at Week 24).
- Group 2 (N=300): Dupilumab 300 mg administered by subcutaneous injection every other week (with a loading dose of 600 mg at baseline) and abrocitinib-matching placebo administered orally QD from Day 1 to Week 26 (the last injection of dupilumab will occur at Week 24).

Rescue Therapy for Atopic Dermatitis

- After Week 4, if medically necessary, participants with intolerable AD symptoms may receive locally-approved rescue therapy, at the investigator’s discretion.
- Participants receiving topical or systemic rescue therapy may continue to receive study intervention concurrently. Participants receiving rescue therapy should continue study visits and assessments.

Sample Size Determination

A total sample of 600 participants, with 300 participants randomized to abrocitinib, 300 participants randomized to dupilumab (1:1 randomization) is planned. The proposed sample size provides adequate power for all superiority hypotheses, as follows:

Week 2: This sample size would provide at least 99% power to detect a difference assuming a difference of at least 25% in PP-NRS response between abrocitinib and dupilumab and the dupilumab response rate is 11% at Week 2.

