Appendix 8. Additional Analyses (Not for CSR Purpose)

The following analyses will be produced at the same time with CSR tables, but will be used for publication or internal reporting purpose, and generally not to be reported in the CSR.

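### Read literally, the baseline filter in SAP Appendix 8.2.2 keeps every participant who already meets the MOS-Sleep optimal-hours response, and the coding of that score is not stated

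*SAP*

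**What the plan says.** SAP Appendix 8.2.2 lists supplementary binary endpoints, to be analysed in the full analysis set (FAS) under Estimand 1 with the CMH method. The last one listed is "Baseline, Weeks 12, 16 and 26 Response based on achieving MOS-Sleep Scale Optimal Hours Slept Score of 1". It is the only endpoint in that list with Baseline among its time points.

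The analysis-set bullet then gives one rule. It covers "Analyses for binary endpoints that are defined based on reaching a threshold of absolute level" as well as endpoints defined by a change from baseline, and says these "will also require baseline value to be equal to or greater than that threshold". The two worked examples are PP-NRS below 2, which needs a baseline of at least 2, and a POEM improvement of at least 4 points, which needs a baseline of at least 4. MOS-Sleep is neither exempted nor given a rule of its own.

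On the instrument, Protocol Section 8.1.6.7 says: "The Medical Outcomes Study Sleep Scale (MOS-Sleep) is a validated 12-item measure". Neither document says how the optimal-hours score is coded.

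On the use of these analyses, the opening of SAP Appendix 8 says they "will be used for publication or internal reporting purpose, and generally not to be reported in the CSR".

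**The concern.** A baseline filter on a responder endpoint normally limits the analysis to participants with room to improve. For most absolute-level endpoints in the list, such as "Weeks 2, 12, 16, 20 and 26 DLQI < 2 Response", a low score is good, so a baseline at or above the cut-off means the participant is not yet a responder. The MOS-Sleep target is different: response means attaining a score of 1, not falling below a cut-off. Applying the same inequality lets existing responders in.

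At stake is what the table would measure. An analysis described as achieving optimal sleep could in fact show how many participants keep it, on a denominator that leaves out those with disturbed sleep. A reader of a publication would have no way to see this from the endpoint's label.

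**Working it through.** The documents give no sample size, power or response rate for this endpoint, so there is no figure of the plan's to reproduce. The check is logical, followed by an illustration.

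**Inputs**
- Response: baseline score *b* = 1 for MOS-Sleep; *b* < *t* for the low-is-good endpoints (SAP Appendix 8.2.2).
- Filter: keep if *b* ≥ *t* (same place).
- Planned size: 600, allocated 1:1 (SAP Section 2.2: "A total sample of 600 participants, with 300 participants randomized to abrocitinib").
- Coding of the optimal-hours score: not given. A 0/1 indicator with 1 as optimal is assumed first, then varied.
- Share with score 1 at baseline: not given. Assumed 20% to 60%.

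**Step 1. Low-is-good endpoints.** Response is *b* < *t* and the filter is *b* ≥ *t*. The two sets are complements, so the filter keeps no baseline responder and drops no non-responder, whatever the range of the scale. This holds for PP-NRS < 2, DLQI < 2, SCORAD sleep-loss VAS < 2, POEM < 3, HADS < 8 and %BSA < 5%.

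**Step 2. MOS-Sleep, any numeric coding.** Response is *b* = 1 and the filter is *b* ≥ 1. Every *b* = 1 satisfies *b* ≥ 1, so all baseline responders are kept. Anyone dropped has *b* < 1 and is therefore a non-responder.

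**Step 3. MOS-Sleep, by coding.**

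| Coding | Kept | Baseline responders among those kept | Non-responders dropped |
|---|---|---|---|
| 0/1, 1 = optimal | 1 | all | all (score 0) |
| 1/2, 1 = optimal | 1 and 2 | some | none |

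Under 0/1 coding the Baseline response rate is (number with score 1) / (number with score 1) = 100% in each arm by construction.

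**Step 4. Illustration under 0/1 coding, N = 600.**

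| Rule for this endpoint | Kept at 20% share | Kept at 60% share | Baseline rate |
|---|---|---|---|
| Filter as written (*b* ≥ 1) | 600 × 0.20 = 120 | 600 × 0.60 = 360 | 100% |
| Baseline score not 1 | 600 − 120 = 480 | 600 − 360 = 240 | 0% |
| Exempt from filter | 600 | 600 | 20% to 60% |

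Only exemption makes the listed Baseline time point informative.

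**The case against.** The strongest reply is that the filter was never meant for this endpoint. The other absolute-level items with a numeric cut-off are written as inequalities, whereas MOS-Sleep is an exact score, closer in form to the category endpoint of a clear IGA. The Baseline time point appears only here and makes sense only if no filter is applied. This is a fair reading of intent and probably the right one. But the text contains no exemption, and attaining a given score is naturally an absolute-level response. Two programmers could reasonably produce different denominators, and the one who followed the rule as written would produce the wrong one.

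Second, the coding is not printed. This stands. A reader might infer that the plan certainly excludes everyone who could improve and certainly yields 100% against 100% at Baseline. The documents do not support that as fact: both results need non-optimal sleep to be coded below 1. What holds under any coding is that existing responders are kept.

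Third, a reader might infer that participants with disturbed sleep drop out of the trial's sleep comparison, or that the table is bound for publication. Neither follows. Change from baseline in MOS-Sleep at Weeks 12, 16 and 26 is a secondary endpoint, analysed by MMRM in all FAS participants with an observed baseline (SAP Section 6.2.2.2). Sleep-loss VAS is analysed separately in Appendices 8.2.2 and 8.2.3. Appendix 8 allows internal reporting as an alternative to publication. The endpoint is outside the testing sequence in SAP Section 5.1, and Section 5.2 rules out significance claims unless an exception is noted.

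**Conclusion.** The point stands in a limited form. As written, the filter does not do for MOS-Sleep optimal hours what it does for the low-is-good endpoints: it keeps every participant who already meets the response. That conclusion rests on the text alone. The more serious consequences, losing everyone who could gain the response and a Baseline rate of 100% in both arms, rest on a 0/1 coding that the wording suggests but neither document confirms. Under that coding the filter cannot be working as intended.

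The counts of 120 to 360 kept and 480 to 240 dropped only illustrate an assumed baseline share; they are not estimates. The effect is confined to one supplementary analysis outside the CSR. No primary, key secondary or other secondary result changes. It is worth correcting because following the stated rule gives a wrong analysis set.

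**What to change.** In SAP Appendix 8.2.2:

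1. State how the MOS-Sleep optimal-hours score is coded.
2. Expressly exempt this endpoint from the baseline filter. Analyse Baseline and Weeks 12, 16 and 26 in all FAS participants with an observed score, so that all time points share one denominator rule. Estimand 1 handling of dropout and rescue stays as it is.
3. If an analysis of participants with room to improve is also wanted, restrict the Weeks 12, 16 and 26 response to those whose baseline score is not 1, and report the Baseline proportion separately. That analysis cannot show loss of optimal sleep, so it should supplement the one in item 2.
4. Keep the existing filter for the endpoints where lower is better.

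The cost is a sentence or so of SAP wording and one changed programming condition. No new data are needed.

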Appendix 8.2.3. Continuous endpoints

- Endpoints:
 - Weeks 2, 4, 8, 12, 16, 20 and 26 Change from Baseline in SCORAD (VAS) of Sleep Loss, SCORAD (VAS) of itch
 - Weeks 2, 4, 8, 12, 16, 20 and 26 Percent Change from Baseline in PP-NRS, EASI, EASI (excluding scalp, palms and soles of feet) and %BSA (excluding scalp, palms and soles of feet)
 - Weeks 1~26 Percent Change from Baseline in PP-NRS (based on weekly average)
- Estimand strategy: Estimand 2, hypothetical estimand (Section 2.1.2).
- Analysis set: FAS (Section 4). Participants must have observed baseline measure to be included in the corresponding analysis.
- Analysis methodology: MMRM (Section 5.2.3) including change from baseline or percent change from baseline data from the corresponding weeks.

Appendix 8.2.4. Hand Eczema

- For hand eczema details at screening, the number and percent will be presented for question 1~22 categories in each treatment arm and treatment arms combined.
 - The denominator for question 1 and 22 will be the number of subjects in FAS.
 - The denominator for question 2 ~ 21 will be the number of subjects with hand eczema (selected 'Yes' in question 1 "Does the participant have hand eczema").
- At Baseline and Weeks 2, 4, 8, 12, 16, 20 and 26, the number and percent will be presented for hand eczema IGA score, and hand eczema IGA score by screening hand eczema type ('Acute' vs 'Chronic').

- Weeks 2, 4, 8, 12, 16, 20 and 26 hand eczema IGA score of clear (0) or almost clear (1) (on a 5-point scale) and a reduction from baseline of ≥ 2 points, and hand eczema IGA response by screening hand eczema type ('Acute' vs 'Chronic').
 - Estimand strategy: Estimand 1, composite estimand.
 - Analysis set: FAS (Section 4) with baseline hand eczema IGA ≥ 2 .
 - Analysis methodology: CMH method.

Appendix 8.2.5. Asthma Control Questionnaire (ACQ)

- The details of ACQ is specified in protocol section 8.1.6.9. The ACQ score is derived by a simple average of the non-missing questions.
- Descriptive summaries will be provided for ACQ score at baseline, Weeks 12 and 26; and for change from baseline ACQ score at Weeks 12 and 26.
- Weeks 12 and 26 Response based on achieving ≤ 1 ACQ score for subjects with ≥ 1.5 ACQ score at baseline
- Weeks 12 and 26 Change from Baseline in ACQ score
 - Estimand strategy: Estimand 2, hypothetical estimand (Section 2.1.2).
 - Analysis set: FAS (Section 4). Participants must have observed baseline measure to be included in the analysis.
 - Analysis methodology: MMRM (Section 5.2.3) with modification: baseline IGA will not be included as a covariate.

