6.3. Measures to Minimize Bias: Randomization and Blinding

6.3.1. Allocation to Study Intervention

Allocation of participants to treatment groups will proceed through the use of an IRT system (interactive Web-based response [IWR]). The block randomization method will be used, and participants will be stratified by baseline disease severity (IGA = 3 vs. IGA = 4). The site personnel (study coordinator or specified designee) will be required to enter or select information including but not limited to the user's identification (ID) and password, the protocol number, and the participant number. The site personnel will then be provided with a treatment assignment, randomization number, and dispensable unit (DU) or container number when study intervention is being supplied via the IRT system. The IRT system will provide a confirmation report containing the participant number, randomization number, and DU or container number assigned. The confirmation report must be stored in the site's files.

Study intervention will be dispensed at the study visits summarized in the [SoA](#).

Returned study intervention must not be re-dispensed to the participants.

The study-specific IRT reference manual and IP manual will provide the contact information and further details on the use of the IRT system.

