8.1.6.9. Asthma Control Questionnaire (ACQ)

Asthma control for all participants with a history of asthma, regardless of whether they are receiving medication for their asthma, should be assessed at times specified in the [Schedule of Activities \(SoA\)](#) using the Asthma Control Questionnaire (ACQ). The ACQ measures the adequacy of asthma control and change in asthma control which occurs either spontaneously

or as a result of treatment. The ACQ has 6 questions and participants are asked to recall how their asthma has been during the previous week and to respond to the symptom questions on a 7-point scale (0 = no impairment, 6 = maximum impairment). The questions are equally weighted and the ACQ score is the mean of the 6 questions and, therefore, between 0 (totally controlled) and 6 (severely uncontrolled).^{54, 55, 56}

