3.5. Baseline Variables

In general, for all analyses, baseline will be defined based on observations collected prior to first dose if dosing time is available. For DLQI, EQ-5D-5L, HADS and POEM, baseline will be defined based on observations collected on or prior to the day of first dose. Baseline values for demographics, medical and other history, atopic dermatitis history will be based on measures collected at Visit 1/Screening visit. Study Day 1 is defined as the day the participant receives first dose of study drug. For purposes of all other analyses including analyses for change from baseline, the baseline value will be defined as measured on Day 1. If a value is missing on Day 1, then the last available observation before Day 1 will be used.

For all analyses described in Section 5.2 where baseline disease severity (IGA = moderate vs severe) is used as a stratum or covariate, if a subject is erroneously enrolled with baseline IGA = mild, they will be considered as moderate IGA in the strata or covariate.

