5.2.3. Analyses for Longitudinal Continuous Endpoints

Mixed-effect, repeated measures (MMRM) models will be used. The fixed effects of treatment, visit, treatment-by-visit interaction and baseline disease severity will be included. Visit will be modeled as a categorical covariate. Unstructured covariance matrix will be assumed for the model errors. Compound symmetry covariance matrix will be used if the model with unstructured covariance doesn't converge.

When modeling the change from baseline values, the variable for visit will start with the first post-baseline visit, and the actual baseline value will be included as a covariate. At each visit, estimates of least square mean (LSM) values and the LSM differences between treatment groups will be derived from the model. The corresponding p-values and 95% confidence intervals will also be derived from the model. Graphs will describe the LSM over time.

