Appendix 8.1. Definitions

Appendix 8.1.1. PP-NRS Weekly Average

PP-NRS is recorded every day throughout the study. PP-NRS (Weekly Average) is defined as the simple average of observed measures within a week. If two or more values are collected on the same day, the last measurement of the day will be used for calculating the average. There should be at least 4 days of observed PP-NRS within a specified week to calculate the average; otherwise the weekly average is set to missing

$$\text{Baseline} = \text{avg}(\text{PP-NRS Day } -6 \sim \text{Day } -1, \text{ Day } 1)$$

$$\text{Week } 1 = \text{avg}(\text{PP-NRS Day } 2 \sim \text{Day } 8)$$

$$\text{Week } 2 = \text{avg}(\text{PP-NRS Day } 9 \sim \text{Day } 15)$$

...

$$\text{Week } [k] = \text{avg}(\text{PP-NRS Day } [7k-5] \sim \text{Day } [7k+1]), 2 < k < 26$$

...

$$\text{Week } 26 = \text{avg}(\text{PP-NRS Day } 177 \sim \text{Day } 183)$$

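### The ACQ change-from-baseline MMRM drops baseline IGA, the randomisation stratification factor, without a reason; secondarily, the ACQ score has no minimum number of answered items

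*SAP*

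**What the plan says.** **Model.** SAP 5.2.3 sets the standard model for longitudinal continuous endpoints: "The fixed effects of treatment, visit, treatment-by-visit interaction and baseline disease severity will be included". For change from baseline, "the actual baseline value will be included as a covariate" as well. SAP 3.5 identifies the severity term as IGA where "baseline disease severity (IGA = moderate vs severe) is used as a stratum or covariate". Protocol 6.3.1 stratifies randomisation by baseline IGA 3 versus 4 and names no other factor. SAP Appendix 8.2.5 then applies 5.2.3 to change in ACQ at Weeks 12 and 26 "with modification: baseline IGA will not be included as a covariate". Baseline ACQ stays in the model. The other MMRMs in the SAP (6.2.2.2 and Appendix 8.2.3) use 5.2.3 unmodified.

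**Score.** Protocol 8.1.6.9 says that "the ACQ score is the mean of the 6 questions", each scored 0 to 6. SAP Appendix 8.2.5 says: "The ACQ score is derived by a simple average of the non-missing questions". It gives no minimum. The same appendix defines a responder as a score of 1 or less among participants whose baseline score is at least 1.5. For the weekly itch average, Appendix 8.1.1 does set a floor: "There should be at least 4 days of observed PP-NRS within a specified week to calculate the average". SAP 5.3.2 refers continuous patient-reported outcomes to the instrument developers' rules, but ACQ is not among its examples.

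**Status.** Appendix 8 describes these analyses as being for publication or internal reporting and generally not for the clinical study report. ACQ is not a listed endpoint in Protocol Section 3 or SAP Table 2.

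**The concern.** A factor used to stratify randomisation normally stays in the model, and this SAP follows that practice in its other MMRMs. The exception is made in a subset defined by an asthma history. Asthma was not a randomisation factor, so severity is balanced between arms within that subset only on average. If IGA is prognostic for ACQ change, leaving it out puts its variation into the residual and leaves any realised imbalance in the estimate.

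The scoring rule raises a separate, smaller question. Read literally, one answered item is a full ACQ score. The two responder cut-offs are only 0.5 apart, whereas a single item moves in whole points.

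**Working it through.** The documents give no sample size, SD, expected effect or power for ACQ, so there is no stated figure to reproduce. All values of r, n, severe share, item SD and inter-item correlation below are assumptions.

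**1. Standard error.** One-visit ANCOVA approximation to the MMRM, with baseline ACQ in both models. Let r be the correlation of IGA with ACQ change after baseline ACQ, and n the total number in the asthma subset.

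- SE ratio (omit/include) = 1/sqrt(1 − r²).
- 95% CI width ratio (omit/include) = t(0.975, n−3) / [t(0.975, n−4) × sqrt(1 − r²) × sqrt(1 + 1/(n−5))]. This charges the extra parameter to the model that keeps IGA.

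| r | SE ratio | CI ratio, n=60 | CI ratio, n=120 | CI ratio, n=180 |
|---|---|---|---|---|
| 0 | 1.000 | 0.9906 | 0.9956 | 0.9971 |
| 0.1 | 1.005 | 0.9956 | 1.0006 | 1.0021 |
| 0.2 | 1.021 | 1.0111 | 1.0161 | 1.0177 |
| 0.3 | 1.048 | 1.0385 | 1.0437 | 1.0453 |

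Omission therefore inflates the SE by 0.5% to 4.8% for r from 0.1 to 0.3. At r = 0, keeping IGA widens the interval by 1/0.9906 − 1 = 0.9% at n=60 and 0.3% at n=180. At n=60 and r = 0.1, keeping it still widens the interval by 0.4%.

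**2. Simulation** (4,000 runs per setting, n = 60 and 120 in total, 40% severe, arms balanced within IGA strata, r from 0 to 0.4). The model SE ratio follows the formula. The actual sampling SD of the estimate is the same with and without IGA (ratio 0.999 to 1.001). When strata are balanced, omission only overstates the SE.

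**3. Chance imbalance.** The asthma subset need not be balanced within strata. With 40% severe and n per arm, the SD of the difference in severe share is sqrt(2 × 0.4 × 0.6/n). This is 8.9 percentage points at 60 per arm and 7.3 at 90. At r = 0.3 the severe-minus-moderate gap is 0.3/sqrt(0.4 × 0.6) = 0.61 SD. A one-SD imbalance at 60 per arm then moves the estimate by 0.61 × 0.089 = 0.055 SD, against an SE of sqrt(2/60) = 0.18 SD. At r = 0.1 the shift is about 0.02 SD.

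**4. Scoring.** With one item answered, an answer of 2 or more meets the 1.5 entry rule, and an answer of 0 or 1 meets the response rule. A one-step change on one item can then make a responder. The error SD of a k-item mean against the six-item mean is sqrt[s²(1 − ρ)(1/k − 1/6)]. With item SD s = 1.2 and inter-item correlation ρ = 0.6, s²(1 − ρ) = 0.576:

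| Items answered | Error SD |
|---|---|
| 1 | 0.69 |
| 3 | 0.31 |
| 4 | 0.22 |
| 5 | 0.14 |

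Even one blank can matter near a cut-off. Items 2,1,1,1,1,1 average 7/6 = 1.17 (non-responder), but 5/5 = 1.00 (responder) if the 2 is missing. With all six items answered, the protocol and SAP rules give the same score.

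**The case against.** The strongest case against is that nothing in the documents shows that skin severity predicts change in asthma control once baseline ACQ is in the model. At r = 0 nothing is lost, and dropping a skin score from an asthma model is an explicit, prespecified choice. That stands as a limit on the claim. A reader might infer that the ACQ effect as planned is less precise, or is biased. The documents support neither: the first depends on an unknown correlation, and randomisation protects against systematic imbalance.

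It also stands that chance imbalance and a larger SE are not two separate harms, because the unadjusted SE already allows for chance imbalance on average. What adjustment adds is correction of the imbalance that actually occurs, and step 3 shows that this is small.

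SAP 6.4 presents subgroup results without severity adjustment, which might look like a precedent. It is a weak one: the primary and key secondary endpoints summarised there are binary, and the section disclaims inference within subgroups. The ACQ MMRM reports a model-adjusted treatment effect.

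On scoring, Protocol 8.1.6 has site staff check questionnaires for completeness before the visit proceeds, so partial forms should be uncommon. A reader might infer that single items will commonly decide response; the documents give no rate and point the other way. The check still does not say how a partial form is scored. SAP 5.3.2 might be read as supplying the developer rule, but Appendix 8.2.5 gives ACQ a rule of its own.

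**Conclusion.** The unexplained removal of the stratification factor is a real inconsistency, worth correcting at low priority. The SE inflation is roughly 0.5% to 5% if r lies between 0.1 and 0.3, and nil if r is zero. The cost of keeping IGA is one degree of freedom, at most about a 0.9% wider interval with 60 participants in total. The point applies only to the change-from-baseline MMRM; Appendix 8.2.5 names no analysis method for the ACQ responder endpoint.

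The missing item floor is a secondary gap. It could misclassify a participant with a largely blank form, but how often cannot be estimated from the documents. Neither point touches the primary or key secondary analyses or the testing sequence.

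**What to change.** 1. In SAP Appendix 8.2.5, delete the modification so that baseline IGA (moderate/severe) stays in the ACQ MMRM as in 5.2.3.
2. In the same appendix, state the minimum number of answered items for a valid ACQ score, set the score to missing below it, and reconcile the wording with Protocol 8.1.6.9. The documents do not fix the number. A majority (4 of 6) would match the spirit of the 4-of-7-day rule in Appendix 8.1.1; adopting the developer rule, as 5.3.2 does for other instruments, would also serve. A floor limits misclassification near the cut-offs but does not remove it.

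The cost is two lines of SAP wording, one degree of freedom, and a missing score for the rare form below the minimum. No new data are needed. Both changes should be made before unblinding.
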